2.5.2. Final Analyses and Reporting

All analyses identified in this Statistical Analysis Plan will be performed after the end of study as defined in the study protocol.

This final version of the Statistical Analysis Plan and any corresponding amendments will be approved before database lock, in accordance to SOP GBP_RD_702 (Statistical Analysis Plan).

The randomization codes will not be unblinded until this Statistical Analysis Plan has been approved and issued.

3. ANALYSIS SETS

3.1. Intent-to-Treat Analysis Set

The intent to treat (ITT) analysis set will include all randomized patients.

In the ITT analysis set, treatment will be assigned based on the treatment to which patients were randomized, regardless of which treatment they actually received.

For patients who discontinue the study and re-enter it (repeating the study from baseline; see Section 4.5), only the data from the repeated participation will be included in the ITT analysis set.

3.2. Modified Intent-to-Treat Analysis Set

The modified intent-to-treat (mITT) analysis set is a subset of the ITT analysis set including all randomized patients with at least 1 post-baseline centrally read MD-CRS part II assessment.

In the mITT analysis set, treatment will be assigned based on the treatment to which patients were randomized, regardless of which treatment they actually received.

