1. STUDY OBJECTIVES

1.1. Primary Estimand

The primary estimand is the difference in means between TEV-50717 and placebo in the target patient population for the change from baseline to week 15 in centrally read Movement Disorder-Childhood Rating Scale (MD-CRS) part II total score, regardless of whether or not dose reduction, suspension, or discontinuation occurred, and regardless of treatment-related adverse events.

The primary estimand assesses the effectiveness in the reduction of choreiform movements in patients with dyskinesia in cerebral palsy (DCP) with predominant choreiform movement disorder, focusing on the causal effects attributable to the investigational medicinal product (IMP).

The target patient population for this study is patients with DCP with predominant choreiform movement disorder and severity of DCP represented by the following:

- a. total score of ≥ 10 in centrally read MD-CRS part II items at baseline, and
- b. Clinical Global Impression of Severity (CGI-S) ≥ 4 at baseline.

This population is expected to have the sensitivity to demonstrate clinically meaningful improvement following treatment with TEV-50717.

Due to practical reasons (periodical assessments), it is not possible to obtain a central reading of MD-CRS part II items at the time of the baseline visit prior to randomization; therefore, inclusion of the patient to the study is based on investigator scoring of MD-CRS part II items at baseline.

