2.4. Sample Size and Power Considerations

The initial sample size estimation of approximately 185 patients randomized to TEV-50717 versus placebo in a 2:1 ratio (approximately 124 in the TEV-50717 group; approximately 61 in the placebo group) is the sample size required to obtain a statistically significant result in the primary analysis based on a 1-sided test for mean difference at a significance level of $\alpha=0.025$ with a power of approximately 90%, assuming a mean difference of 1.8 and a standard deviation (SD) of 3.5 in each treatment group.

Based on Protocol Amendment 05, the initial planned sample size has been reduced to approximately 65 patients randomized to TEV-50717 versus placebo in a 2:1 ratio (approximately 43 in the TEV-50717 group; approximately 22 in the placebo group).

The initial assumptions regarding the mean difference and SD are based on the change from baseline to month 6 in patients treated with trihexyphenidyl reported by [Battini et al \(2014\)](#), assuming an effect size of 55% for TEV-50717 versus placebo. The effect size of 55% was assumed based on the observed effect sizes of TEV-50717 in the pivotal studies in Huntington's disease and tardive dyskinesia. In the current study, these assumptions correspond to a mean difference of 2.0 in MD-CRS part II total score and an SD of 3.5 in each treatment group.

The rate of missing not at random (MNAR) data for the primary analysis is expected to be 10%. MNAR data will be imputed in a conservative manner as if they were obtained from patients in the placebo treatment group, regardless of the actual treatment group. As a result, the mean difference is expected to be reduced from 2.0 to 1.8 in the primary analysis. The impact of the missing data imputation on the SD is negligible.

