6. EFFICACY ANALYSIS

6.1. General

The mITT, mITTA, mITTB, ITT, and PP analysis sets (Section 3) will be used for all the efficacy analyses.

The mITT analysis set will be regarded as the main set for the analysis of the primary endpoint. It will also be used for all the efficacy endpoints unless otherwise specified. In addition, the mITTA, mITTB, ITT, and PP analysis sets will be used for the sensitivity analyses of the primary and key secondary endpoints.

Summaries will be presented by each scheduled visit (until Week 15) and treatment group, unless specified otherwise.

All p-values for treatment effect (TEV-50717 vs. placebo) will correspond to a 1-sided test for superiority.

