6.2.3. Primary Efficacy Analysis

The primary analysis will be a mixed-model repeated-measures (MMRM) with the change in MD-CRS part II total score as the dependent variable. The model will include fixed effects for treatment group, week (as a categorical variable with 3 levels: weeks 9, 12, and 15), and treatment group by week interaction. The baseline MD-CRS part II total score, age group at baseline (2 levels: 6 to <12 years; 12 through 18 years, inclusive), and region (US; non-US) will be included as covariates. The unstructured covariance matrix will be used in the model. In cases where the model does not converge, the Maximum-Likelihood estimation method will be used instead of the default Restricted Maximum-Likelihood. If the model still does not converge, then a simpler covariance structure with fewer parameters will be used, according to the following order: Heterogeneous Autoregressive (1), Heterogeneous Compound Symmetry, Autoregressive (1), and Compound Symmetry. The Kenward-Roger approximation will be used to estimate denominator degrees of freedom.

Missing data will be classified as MAR and MNAR, as described in Section 4.3. MNAR data will be imputed using the jump-to-reference method, and MAR data will be imputed based on the randomized treatment group. The details are described below:

1. Missing data will be imputed in 2 separate subgroups. The MAR subgroup will contain all patients randomized to a TEV-50717 treatment group without missing data at week 15 or have a MAR missing data mechanism. The MNAR subgroup will contain all patients randomized to placebo as well as patients randomized to receive TEV-50717 with missing data at week 15 with an MNAR missing data mechanism.
2. Data will be imputed for patients with missing data at week 15 using a predictive mean matching multiple imputation method. Multiple imputations will be performed within each subgroup:
 - a. Under a MNAR data assumption, patients in the MNAR subgroup will have their missing data at week 15 imputed as if they behaved like placebo treated patients after dropping out. Only placebo patients with complete data will be included in the imputation model.
 - b. All other patients will have data imputed from a model derived from their assigned treatment group (imputation under MAR assumption).

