10.4. Estimation of Conditional Power

The conditional power is the probability of rejecting the null hypothesis at the final analysis, assuming the alternative hypothesis is true given the data accumulated in the interim analysis. Conditional power will be estimated given the observed data, under the following assumptions:

- effect size (true difference and standard error) is as estimated in the observed data (point estimates)
- proportion of missing data MNAR in the TEV-50717 treatment group is as in the observed data
- proportion of patients excluded from the mITT analysis set is as in the observed data

Note: the conditional power is estimated based on the observed data and does not take into account the initial assumptions that were used for estimating the initial sample size.

The primary analysis is a 1-sided test of the null hypothesis $H_0: \delta \geq 0$ versus the alternative hypothesis $H_1: \delta < 0$, where δ is the difference between TEV-50717 and placebo in change from baseline in centrally-read MD-CRS part II total score (higher score represents a more severe movement disorder, thus negative change from baseline is a good outcome).

Let n_1 be the number of patients included in the mITT analysis set in the IA, and let n_2 be the incremental number of patients between the IA and the final analysis that will be included in the mITT analysis set, such that the total number of patients in the analysis will be $n = n_1 + n_2$.

Let z_1 be the Wald statistic at the IA. The conditional power is given by (Mehta and Pocock 2011):

$$\text{CPow}(n_2|n_1, z_1) = 1 - \Phi\left(\frac{z_\alpha\sqrt{n} - z_1\sqrt{n_1}}{\sqrt{n_2}} - \frac{z_1\sqrt{n_2}}{\sqrt{n_1}}\right)$$

Calculation of the Wald statistic:

$$z_1 = \frac{-\hat{\delta}_1}{\text{se}(\hat{\delta}_1)}$$

Where, $\hat{\delta}_1$ is the estimated mean difference between TEV-50717 and placebo and $\text{se}(\hat{\delta}_1)$ is the estimated SE of the mean difference, both obtained from the primary analysis model (MMRM applying MAR/MNAR multiple imputation; see Section 6.2.3) fitted to the IA mITT data.

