APPENDIX 1. MAR/MNAR JUMP TO REFERENCE MULTIPLE IMPUTATION METHODOLOGY

The following 3 steps will be performed to do the multiple imputation analysis:

1. Create complete data sets using imputation for each subgroup.
2. Analyze the imputed complete data sets for the combined subgroups.
3. Combine analysis results into a final result.

Step 1

In order to induce monotonicity, an imputation model will first be used to impute missing values for MD-CRS part II total score week 9, 12, and 15 change values and will use age group at baseline and baseline MD-CRS part II total score to determine the scores (500 imputations will be created).

The SAS code for the imputation is as follows:

```
proc mi data=final out=mitv1 seed=987 nimate=500;
  where arm='TEV-50717' & (missdm in ("MAR") or _9^=.); /* 1st subgroup */
  class agegrp region;
  var agegrp region base _9;
  monotone regpmm; run;

proc mi data=final out=miplb1 seed=876 nimate=500;
  where arm='PLACEBO' or (arm='TEV-50717' & missdm='MNAR' & _9=.); /* 2nd subgroup */
  class agegrp region;
  var agegrp region base _9;
  monotone regpmm; run;

data mi1; set mitv1 miplb1; run;

proc sort data=mi1; by _imputation_; run;

proc mi data=mi1 out=mitv2 seed=9876 nimate=1; by _imputation_;
  where arm='TEV-50717' & (missdm in ("MAR") or _12^=.);
  class agegrp region;
  var agegrp region base _9 _12;
  monotone regpmm; run;

proc mi data=mi1 out=miplb2 seed=8765 nimate=1; by _imputation_;
  where arm='PLACEBO' or (arm='TEV-50717' & missdm='MNAR' & _12=.);
  class agegrp region;
  var agegrp region base _9 _12;
  monotone regpmm; run;

data mi2; set mitv2 miplb2; run;

proc sort data=mi2; by _imputation_; run;

proc mi data=mi2 out=mitv3 seed=98765 nimate=1; by _imputation_;
  where arm='TEV-50717' & (missdm in ("MAR") or _15^=.);
  class agegrp region;
```

```
var agegrp region base _9 _12 _15;  
monotone regpmm; run;
```

```
proc mi data=mi2 out=miplb3 seed=87654 nimpute=1; by imputation;  
where arm='PLACEBO' or (arm='TEV-50717' & misdm='NMAR' & _15=.);  
class agegrp region;  
var agegrp region base _9 _12 _15;  
monotone regpmm; run;
```

Step 2

The resultant complete data sets will be combined for the 2 subgroups and then analyzed using mixed-model, repeated-measures with the change in MD-CRS part II total score as the dependent variable (the primary analysis). The SAS code is as follows:

```
data all; set mitv3 miplb3;  

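### Randomised patients with no usable post-baseline central MD-CRS part II reading drop out of the primary, key secondary and interim analyses, although the estimand counts patients regardless of discontinuation

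*SAP*

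**What the plan says.** Section 3.2 defines the mITT set as a subset of ITT, "including all randomized patients with at least 1 post-baseline centrally read MD-CRS part II assessment". Section 6.1 states: "The mITT analysis set will be regarded as the main set for the analysis of the primary endpoint". It also uses mITT for the other efficacy endpoints unless something else is specified. The interim Wald statistic in Section 10.4 is "fitted to the IA mITT data", and conditional power assumes that the "proportion of patients excluded from the mITT analysis set is as in the observed data".

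The primary model in Section 6.2.3 includes "week (as a categorical variable with 3 levels: weeks 9, 12, and 15"), so the first scheduled post-baseline reading is at week 9, after the 7-week titration. Section 2.1 asks for an early-termination visit after withdrawal. Table 2 in Section 4.4 assigns an early-termination MD-CRS on days 2 to 73 to week 9.

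The primary estimand in Section 1.1 holds "regardless of whether or not dose reduction, suspension, or discontinuation occurred". Section 4.3 classes early terminations for tolerability, treatment-related adverse events or lack of efficacy as MNAR. Section 6.2.3 imputes these from placebo patients. Section 2.4 builds this into the design with a 10% MNAR rate: "As a result, the mean difference is expected to be reduced from 2.0 to 1.8 in the primary analysis". ITT appears only among the sensitivity analyses (Sections 6.1, 6.2.4 and 6.2.4.3).

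**The concern.** Whether a randomised patient counts in the confirmatory test depends on something that happens after randomisation: that at least one video could be read centrally. A patient who stops during titration and has no readable early-termination assessment is removed, not imputed. If the reason was tolerability or lack of efficacy, this is the kind of patient for whom the plan intends placebo-like imputation.

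The exclusion reaches further than the primary endpoint. CaGI-I and CGI-I are modelled from week 3 (Section 6.3.1.1). A patient with week 3 and week 7 ratings but no MD-CRS part II reading still leaves those two key secondary tests, because membership depends on a different scale.

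The SAP expects such exclusions. Section 5.1 provides for more than 10% of ITT falling outside mITT, and Section 10.5 scales the total sample size for them. With 43 and 22 patients per arm, a handful matters.

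**Working it through.** **1. The plan's own figures.** Inputs from Section 2.4: difference 2.0, reduced to 1.8; SD 3.5; one-sided alpha 0.025; power about 90%; 124:61 initially, 43:22 now.

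- Penalised difference: 2.0 × (1 − 0.10) = 1.8.
- Placebo group size at 2:1: 1.5 × (1.960 + 1.282)² × 3.5² / 1.8² = 59.6, so 60 and 180 in total, against about 185 stated.
- Power at 124:61: SE = 3.5 × √(1/124 + 1/61) = 0.547; 1.8/0.547 − 1.960 = 1.33, so 90.8%.

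The stated design reproduces.

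**2. What the mITT rule does to the 1.8.** Suppose that 10% of randomised active patients are MNAR, and that a share f of them has no post-baseline reading. Those patients leave mITT, and the rest are imputed as placebo. As in Section 2.4, each imputed patient contributes a zero difference. Then

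mITT difference = 2.0 × [1 − (0.10 − 0.10f)/(1 − 0.10f)] = 1.8/(1 − 0.10f).

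With all randomised patients kept and imputed as placebo, the difference is 1.8 whatever f is. At 43:22, SE = 3.5 × √(1/43 + 1/22) = 0.917 and power is 50.1%.

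| f | active patients excluded (of 43) | mITT difference | power, mITT | power, ITT |
|---|---|---|---|---|
| 0 | 0 | 1.80 | 50.1% | 50.1% |
| 0.25 | 1.1 | 1.85 | 51.7% | 50.1% |
| 0.50 | 2.1 | 1.89 | 53.5% | 50.1% |
| 0.75 | 3.2 | 1.95 | 55.3% | 50.1% |
| 1 | 4.3 | 2.00 | 57.1% | 50.1% |

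The lost penalty is 0 to 0.2 points, or 0 to 11% of 1.8. If the MNAR rate were 5%, 15% or 20% and every such patient lacked a reading, the gap would be 0.1, 0.3 or 0.4 points. The SAP gives no value for f.

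**3. Could these patients be imputed instead?** Section 4.3.1 gives every ITT patient a baseline value. The week 9 step in Appendix 1 imputes from age group, region and baseline, and its second subgroup selects "arm='TEV-50717' & missdm='MNAR' & _9" missing. The first subgroup covers active patients classed MAR. Section 6.2.4.3 already plans the primary model on ITT.

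One step fails as printed. The week 15 selection for the second subgroup tests `misdm='NMAR'`, whereas the week 9 and week 12 steps test `missdm='MNAR'`. The first week 15 subgroup takes only active patients who are MAR or have an observed week 15 value. An active MNAR patient with week 15 missing therefore falls into neither.

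**The case against.** **Early-termination readings count.** A reader might infer that everyone who leaves before week 9 is excluded. The SAP does not support that. An early-termination visit is expected, and a reading from day 2 onwards is assigned to week 9. A titration dropout with a readable assessment stays in mITT. Only patients with no usable reading are lost, and their number is unknown.

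**The estimand imposes no penalty.** This stands. Section 1.1 requires that patients count regardless of discontinuation; the placebo-like imputation comes from Sections 2.4 and 6.2.3. Section 2.4 states its 10% for the primary analysis, and Section 10.4 lists the MNAR proportion and the mITT exclusion proportion separately. The 10% can therefore be read as a rate within mITT, in which case 1.8 is undisturbed. The conflict with the estimand remains under either reading.

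**Type I error.** A reader might infer that mITT inflates the error rate and that ITT cures it. The SAP gives no unread rate by arm and no outcome for such patients. As an illustration, assume no drug effect, a 10-point excess of unread active patients, and outcomes 2 points worse than the rest. The mITT bias is 0.20, and 1 − Φ(1.96 − 0.20/0.917) = 4.1%. Placebo imputation in ITT leaves 0.9 × 0.20 = 0.18, which gives 3.9%. About a tenth of the assumed bias goes, so this is no argument for the change.

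**Not all unread patients would be penalised.** Losses to follow-up and COVID-19 terminations are MAR and would be imputed from their own arm.

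**ITT is already planned.** True, but as a sensitivity analysis it does not open the key secondary hierarchy in Section 7 and does not feed the interim statistic.

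**The interim look is non-binding and for futility only** (conditional power below 3%). A more favourable mITT statistic makes stopping less likely and cannot inflate type I error. The interim set matters mainly because it should match the final test.

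**Conclusion.** The point holds for randomised patients with no usable post-baseline central MD-CRS part II reading. They are left out of the primary, key secondary and interim analyses, contrary to an estimand that covers the target population regardless of discontinuation. Those classed MNAR also escape the imputation in Section 6.2.3.

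The size is modest and uncertain: 0 to 0.2 points on an expected 1.8 at 43:22. This rests on the 10% MNAR rate applying to all randomised active patients and on Section 2.4's simplification that an imputed patient shows no difference from placebo. The upper end needs every MNAR patient to lack a reading. The case for change rests on who is counted in the confirmatory test, not on a demonstrated error inflation.

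**What to change.** - In Section 6.1, make ITT (all randomised) the main set for the primary and key secondary analyses. In Section 6.2.4, list mITT as the sensitivity analysis in its place.
- State that patients with no post-baseline reading are imputed through the Appendix 1 branches according to their MAR or MNAR class.
- In Sections 10.2 to 10.5, compute the interim statistic on ITT. The assumption on mITT exclusions and the scaling for them are then no longer needed.
- In Appendix 1, change the week 15 selection from `misdm='NMAR'` to `missdm='MNAR'`. Until this is done, the printed code does not impute these patients at week 15.

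This needs SAP wording and one line of code, with no new data. The price is a slightly smaller expected effect and a few more imputed values. The change must be in place before the interim analysis, because Sections 2.5.1 and 10.1 bar later changes to the main analysis.

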3.3. Safety Analysis Set

The safety analysis set will include all randomized patients who receive at least 1 dose of IMP.

In the safety analysis set, treatment will be assigned based on the treatment patients actually received, regardless of the treatment to which they were randomized, unless otherwise specified.

Rules for assignment of treatment in case of mixed actual treatments:

- If a patient received placebo throughout the entire treatment period, then actual treatment is placebo.
- If a patient was randomized to placebo and received TEV-50717 for up to 7 days, then actual treatment is placebo
- Otherwise, actual treatment is TEV-50717.

For patients who discontinue the study and re-enter it (repeating the study from baseline; see Section 4.5) only the data from the repeated participation will be included in the safety analysis set.

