3.4. Per-Protocol Analysis Set

The per-protocol (PP) analysis set is a subset of the mITT analysis set including only patients who meet the following criteria:

- compliant with study medication (80% to 105%)
- complete the study without any major protocol deviations that may impact efficacy
- centrally read baseline MD-CRS part II total score ≥ 10

Examples of major protocol deviations that may result in patient exclusion from the PP analysis set are given in [Table 1](#).

Table 1: Possible Types of Major Protocol Deviations that May Lead to Exclusion from the Per-Protocol Analysis Set

Type of deviation	Description of Deviation
Informed consent	Missing informed consent
Inclusion/Exclusion	Patient did not meet inclusion/exclusion criteria
Compliance	Overall compliance during the treatment period <80% or >105%
	Overall compliance during the maintenance period <80% or >105%
Study drug	Patient took incorrect dose for more than 7 days
Dosing error	Patient received the incorrect IMP, contrary to the randomization schedule (eg, patient randomized to placebo group and received a supply of TEV-50717).
Restricted/disallowed Concomitant Medication	Patient took a medication that was not permitted during participation in this study
MD-CRS part II total score	Missing centrally-read MD-CRS part II assessment at baseline
	Patient does not have at least 1 post-baseline centrally read MD-CRS part II assessment

Evaluation of exclusion from the PP analysis set will be discussed on a case-by-case basis and documented prior to database lock and unblinding of the study for final analysis.

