8. SAFETY ANALYSIS

8.1. General

Safety analyses will be performed on the safety analysis set (Section 3.3), unless otherwise noted. Summaries will be presented by treatment group and for all patients, unless otherwise stated. Selected safety data might also be presented by age group, as applicable.

For continuous variables, descriptive statistics will be provided for actual values and changes from baseline to each time point. For categorical variables, patient counts and percentages will be provided.

Safety assessments and time points are provided in Table 3 of the study protocol.

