8.3. Adverse Events

Adverse events will be collected and recorded from the time a patient signs the informed consent to the end of follow-up period. For this study, the follow-up period for recording of adverse events is defined as 2 weeks after the last dose of IMP or up to baseline/day 1 in the open-label safety extension study TV50717-CNS-30081 (whichever comes first) or 2 weeks after last site visit for patients who terminated early from the study.

All adverse events will be coded using MedDRA. Each patient will be counted only once in each preferred term or SOC category for the analyses of safety. Unless otherwise specified, adverse events will be summarized by SOC and preferred term, with SOCs and preferred terms within SOCs presented in descending order of patient incidence. Summaries will be presented for all adverse events (overall and by severity), adverse events determined by the investigator to be related to test IMP (ie, reasonable possibility; see Table 7 of the study protocol - defined as related or with missing relationship), overall and by severity, serious adverse events, and adverse events causing withdrawal from the study; Most common adverse events, defined as occurring in $> 4\%$ of the patients in either of the treatment groups overall, and by preferred term. Summaries will be presented by treatment group and for all patients.

Summaries will include treatment-emergent adverse events which are defined as adverse events occurring at or after the first dose of the IMP. The listings will include all adverse events recorded.

Patient listings of all adverse events, serious adverse events, adverse events leading to study drug discontinuation, adverse events leading to dose interruption and adverse events leading to death will be presented. Patient's dose at the time of the AE onset will be included in all listings.

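### A placebo patient who takes TEV-50717 for up to 7 days is analysed as placebo, and no adverse event summary attributes events to the drug taken at onset

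*SAP*

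**What the plan says.** SAP Section 3.3 sets the general principle for the safety set: "treatment will be assigned based on the treatment patients actually received, regardless of the treatment to which they were randomized, unless otherwise specified". It then introduces three bullets with "Rules for assignment of treatment in case of mixed actual treatments":

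- A patient on placebo throughout is placebo.
- "If a patient was randomized to placebo and received TEV-50717 for up to 7 days, then actual treatment is placebo".
- Every remaining mixed case counts as TEV-50717.

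Section 8.1 carries this assignment into the safety tables: "Safety analyses will be performed on the safety analysis set (Section 3.3), unless otherwise noted". Section 8.3 sets the counting window: "Summaries will include treatment-emergent adverse events which are defined as adverse events occurring at or after the first dose of the IMP". The overall, related, serious and withdrawal event summaries are all by treatment group, and each patient counts once per term. Dose at event onset is added to the listings only.

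The SAP foresees the situation. Table 1 in Section 3.4 gives as an example of a dosing error a "patient randomized to placebo group and received a supply of TEV-50717".

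**The concern.** Once a placebo-randomised patient is classed as placebo under the second bullet, all of that patient's events go to placebo, including those that begin on active drug. Three features make this worth attention in a safety analysis.

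- **Direction.** Within this exception, the misplaced events can only move from TEV-50717 to placebo. That raises the comparator rate and narrows the contrast.
- **The cut-off can depend on the outcome.** A mistaken exposure stopped within 7 days because of an adverse event stays under placebo. One tolerated past 7 days moves to TEV-50717. The exposures that ended badly are the ones more likely to remain in the comparator.
- **Loose wording.** The bullet does not require that the patient also took placebo, and it does not say whether the 7 days are consecutive or cumulative.

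What is at stake is how the between-group event rates read in a small paediatric trial. Efficacy and type I error are not affected.

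**Working it through.** The SAP states no figure that depends on this rule, so there is none to reproduce. The effect can be sized from the planned numbers.

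**Inputs**
- Planned group sizes, SAP Section 2.4: about 43 TEV-50717 and 22 placebo.
- Treatment period, SAP Section 2.1: 7 + 8 = 15 weeks, or 15 × 7 = 105 days.
- Number of affected patients: not given. One is assumed below; it may be zero.

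**1. One affected patient, with an event that occurs in nobody else**
- Under the rule: placebo 1/22 = 4.5%, TEV-50717 0/43 = 0%. Difference (TEV-50717 minus placebo) = −4.5 points.
- Patient moved wholly to TEV-50717: 1/44 = 2.3% against 0/21 = 0%. Difference = +2.3 points.
- Swing: 4.5 + 2.3 = 6.8 points.

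**2. Illustration with assumed counts:** 4 events on TEV-50717 and 1 on placebo, plus one affected patient
- Under the rule: 4/43 − 2/22 = 9.3% − 9.1% = 0.2 points.
- Patient moved wholly: 5/44 − 1/21 = 11.4% − 4.8% = 6.6 points.
- Event attributed by drug at onset, with the patient also kept in the placebo denominator: 5/44 − 1/22 = 11.4% − 4.5% = 6.8 points after rounding the difference.

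**3. Share of time on active drug for a completer**
- At most 7/105 = 6.7%, so at least 98/105 = 93.3% of treatment is on placebo.

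**4. The wording, case by case**

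| Randomised | Took | Result under the bullets |
|---|---|---|
| Placebo | Placebo, plus up to 7 days of TEV-50717 | Placebo |
| Placebo | Placebo, plus 8 days of TEV-50717 | TEV-50717 |
| Placebo | Only TEV-50717, 7 days or fewer, then stopped | Placebo on a literal reading; TEV-50717 if the heading and the as-treated sentence govern |
| Placebo | Two separate 5-day spells of TEV-50717 (assumed) | TEV-50717 if cumulative (5 + 5 = 10 days); placebo if each spell is judged alone |
| TEV-50717 | TEV-50717 briefly, otherwise placebo by mistake | TEV-50717 |

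Rows three and four cannot be settled from the text as written.

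**The case against.** The case for leaving the rule alone is substantial.

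- A reader might infer that Section 3.3 contradicts itself by stating an as-treated principle and then using randomised treatment. It does not. The principle allows for exceptions, and a patient with mixed exposure has no single treatment received, so some tie-break is needed. This one is explicit and set in advance.
- A reader might call the whole rule set anti-conservative. It is not: every other mixed case goes to TEV-50717, even one that is mostly placebo. Only this exception runs the other way.
- A reader might picture a wrong maintenance-stage kit taking a placebo patient straight to a high dose. The SAP does not describe kit dispensing, so this is inference. Clinic visits in maintenance are 2 to 3 weeks apart (weeks 7, 9, 12 and 15). If kits follow visits, a wrong kit used until the next visit would exceed 7 days and fall under TEV-50717.
- A reader might stress that 4.5% passes the more-than-4% threshold for common events in Section 8.3. Any single event in any placebo patient does so, whatever this rule says.
- The 6.8-point swing needs a misdosed patient whose event occurred only during the exposure. If the same term also arose on placebo, the patient counts there anyway.
- Deleting the bullet would charge about 93% placebo time to active drug for a completer and reduce the comparator to 21.
- The listings show dose at onset, protocol deviations are listed, and no between-group test of adverse events is planned.

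All of this stands. It rules out calling the bullet an error, and it rules out deletion as the plain remedy. It does not answer the narrower point that no summary table separates events by the drug taken at onset, and it does not settle the two gaps in wording.

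**Conclusion.** The point holds as a modest, inexpensive improvement. The 7-day tolerance is a defensible choice for assigning mixed-exposure patients, but the SAP gives no summary by drug at onset. Any bias within the exception runs towards making TEV-50717 look safer. Each affected patient adds 4.5 points to the placebo rate for an event that began on active drug. This assumes 22 placebo patients and that the same term did not also occur during that patient's placebo time. The expected impact is small because such patients should be rare, and it is nil if there are none. Separately, the bullet as worded reaches a patient who took only TEV-50717, which the heading above it does not intend.

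**What to change.** In SAP Section 3.3, keep the 7-day tolerance for the main assignment of mixed-exposure patients, and:

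1. Restrict the second bullet to patients who also took placebo, so that a patient who took only TEV-50717 is analysed as TEV-50717 whatever the duration.
2. State that the 7 days are cumulative.

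In SAP Section 8.3:

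3. Flag any affected patient in the adverse event tables with a footnote.
4. Add a supplementary table of all, serious and withdrawal events. It counts under TEV-50717 those events with onset from the first mistaken TEV-50717 dose through the end of that exposure plus the 1-week washout, with the patient in that column's denominator. The patient's other events stay under placebo, so the footnote should say that the patient appears in both denominators.

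The cost is a few lines of SAP text, one derivation, and one extra table needed only if such a patient exists. The rule is best fixed before database lock and unblinding.
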